6.1.1 Population per protocol (PP)

The per-protocol population is defined as all patients included in the study without major protocol deviation (i.e. meeting the criterion "Endocrine tumor of the gastrointestinal tract"), having at least one (chemo)embolization and at least 1 month of everolimus treatment (started within 30 days post-HEC).

A listing of patients excluded from the PP population will be provided with the reasons for exclusion.

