Everolimus will be started 7 days after embolization or chemoembolization or when liver toxicities have returned to a grade ≤ 1 according to the NCI CTIC version 4.0 toxicity scale. Treatment should not be initiated beyond 30 days after embolization or chemoembolization.

If embolization or chemoembolization cannot be performed after patient inclusion, everolimus MUST NOT be started.

If embolization or chemoembolization is postponed, wait for embolization or chemoembolization to start everolimus as described above. If embolization or chemoembolization is definitely cancelled, DO NOT ADMINISTER everolimus and follow the patient according to the recommendations (see paragraph VIII-2: monitoring after cessation of treatment).

For the second session, everolimus will be stopped the day before the session and restarted in the same manner as initially, i.e., 7 days after embolization or chemoembolization or when liver toxicities have returned to a grade ≤ 1 according to the NCI CTIC toxicity scale version 4.0 and within a maximum of 30 days after embolization or chemoembolization.

Method of administration

Everolimus should be taken orally once a day at the same time each day, with or without food. The tablets should be swallowed whole with a glass of water. The tablets should not be chewed or crushed.

If a dose is missed, the patient should not take an additional dose, but should take the next prescribed dose.

3- Concomitant treatments to be avoided

Everolimus is a substrate of CYP3A4 and a moderate inhibitor of P-glycoprotein (PgP). Therefore, the absorption and subsequent elimination of everolimus may be influenced by drugs that act on CYP3A4 and/or PgP. In vitro, everolimus is a competitive inhibitor of CYP3A4 and a mixed inhibitor of CYP2D6.

Known and theoretical interactions with selective inhibitors and inducers of CYP3A4 and PgP are described in the Table below.

CYP3A4 and PgP inhibitors that may increase everolimus concentrations: CYP3A4 or PgP inhibitors may increase blood levels of everolimus by decreasing the metabolism or efflux of everolimus from intestinal cells.

CYP3A4 and PgP inducers that may decrease everolimus concentrations: Substances that are CYP3A4 and PgP inducers may decrease blood levels by increasing everolimus metabolism or efflux of everolimus from intestinal cells.

Effect of other active substances on everolimus

Active substances by interaction	Recommendations for Concomitant Administration
Potent CYP3/PgPA INHIBITORS	

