5.7.2.2 Survival without liver progression

It is defined as the time from the date of inclusion to the date of first hepatic progression (based on centralized review or on the investigator's opinion in case of impossible review) or the date of death (regardless of cause). Living patients without hepatic progression will be censored at the point date or the date of last morphological evaluation.

Live patients for whom no morphological evaluation is available will be censored at inclusion date + 1 day.

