5.7.2.3 Progression-free survival

It is defined as the time between the date of inclusion and the date of first hepatic or extrahepatic progression (based on centralized review or on the investigator's opinion in case of unavailable review) or

the date of death (regardless of cause). Patients alive without progression will be censored at the point date or the date of last morphological evaluation.

Live patients for whom no morphological evaluation is available will be censored at inclusion date + 1 day.

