5.7.2.4 Overall survival

It is defined as the time between the date of inclusion and the date of death (regardless of cause). Patients lost to follow-up or alive at the time of analysis will be censored at the date of last news.

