7.5.2 Survival without liver progression

CP, ITT and PP population (if the number of patients allows it)

The time scale considered will be the month.

Progression-free survival will be plotted using the Kaplan Meier estimator. Median survival and rates at different time points will be calculated along with their 95% confidence intervals.

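### Per-protocol survival curves start at inclusion although membership requires a month of everolimus, so early deaths cannot appear in them and the PP curves carry a small upward bias

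*SAP*

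**What the plan says.** **Who is in PP.** SAP 6.1.1 (Population per protocol) requires a digestive-tract endocrine tumour, at least one (chemo)embolization, and "at least 1 month of everolimus treatment (started within 30 days post-HEC" (that is, after the procedure). Exclusions are to be listed with reasons.

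**Where the clock starts.** All three survival times start at inclusion: hepatic PFS is the "time from the date of inclusion to the date of first hepatic progression" or death (SAP 5.7.2.2), PFS is "the time between the date of inclusion and the date of first hepatic or extrahepatic progression" or death (SAP 5.7.2.3), and OS is "the time between the date of inclusion and the date of death (regardless of cause" (SAP 5.7.2.4).

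**Which curves are planned.** SAP 7.5.2, 7.5.3 and 7.5.4 each plan a Kaplan-Meier curve in the "CP, ITT and PP population (if the number of patients allows it". Neither document gives the PP curves a different origin, a landmark or delayed entry.

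**When everolimus starts.** Protocol VI.2: "Everolimus will be started 7 days after embolization or chemoembolization or when liver toxicities have returned to a grade" of at most 1. The same section adds: "Treatment should not be initiated beyond 30 days after embolization or chemoembolization".

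**When progression can be seen.** Protocol VIII.1 schedules CT every 3 months from the first session. A CT before the second session is allowed for technical reasons only and may not be used to judge response. Under Protocol IX, progression or death ends study treatment.

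**The concern.** Membership of PP is decided by something that happens after the survival clock has started. Someone who dies before completing the qualifying month is left out because of that death, while everyone kept in is known to have survived to that point. The early part of the curve is then free of deaths by construction. This is guarantee-time (immortal-time) bias. It would be present even if a month of everolimus did nothing.

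This differs from an ordinary exclusion for not following the protocol. A patient who dies in the first weeks, or whose everolimus is stopped because the protocol's own rules require it, has followed the protocol and is still removed.

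It matters because the trial has one arm and absolute survival rates are its evidence. PP curves will sit beside the ITT and CP curves. A PP curve above the ITT curve invites the reading that patients who really took everolimus did better, and this display cannot separate that from selection.

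**Working it through.** **1. The plan's own figure.** The documents give no figure for the PP curves. The design figure reproduces: with 68 patients and success at 31 or more, the exact one-sided alpha at 35% is 0.0461 and the power at 50% is 0.8019; 68/0.95 = 71.6, hence 72. This rule is applied to the CP set (SAP 5.6.1, 6.1.2, 7.4), so the PP definition does not enter it.

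**2. Length of the guaranteed period.** Inputs: everolimus from day 7 to day 30 after the session (Protocol VI.2; SAP 6.1.1), 1 month of treatment (SAP 6.1.1), 1 month = 30.4375 days (SAP 7.1.3). SAP 7.6.2.1 measures duration from first to last intake without deducting interruptions, so the month is taken as calendar time. The gap from inclusion to first session is not stated; 0 to 28 days is assumed.

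t0 = (gap + start delay + 30.4375) / 30.4375

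- No gap, day 7: 37.4375/30.4375 = 1.23 months
- No gap, day 30: 60.4375/30.4375 = 1.99 months
- 28-day gap, day 30: 88.4375/30.4375 = 2.91 months

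**3. Theoretical upper bound for the PFS curves.** Suppose progression and death are both detected continuously and both bar entry to PP before t0. PP then estimates S(24)/S(t0) instead of S(24). With a constant hazard, λ = -ln S(24)/24, S(t0) = exp(-λ·t0), using the SAP 5.5 rates:

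| True S(24) | λ per month | t0 = 1.23 | t0 = 1.99 | t0 = 2.91 |
|---|---|---|---|---|
| 35% | 0.0437 | 36.9% (+1.9) | 38.2% (+3.2) | 39.7% (+4.7) |
| 50% | 0.0289 | 51.8% (+1.8) | 52.9% (+3.0) | 54.4% (+4.4) |

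Rounding the longest t0 up to 3 months gives 0.35^(21/24) - 0.35 = +4.9 points. The bound is therefore +1.8 to +4.9.

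**4. PFS curves with the actual scan schedule.** No scan is scheduled before month 3 in any population, so what PP removes before t0 is mainly deaths. If deaths are a share d of the hazard, the inflation is S(24) × [exp(d·λ·t0) - 1]. The documents do not give d; 10% and 20% are assumed.

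| True S(24) | d | t0 = 1.23 | t0 = 2.91 |
|---|---|---|---|
| 35% | 10% | +0.19 | +0.45 |
| 35% | 20% | +0.38 | +0.90 |
| 50% | 10% | +0.18 | +0.42 |
| 50% | 20% | +0.36 | +0.85 |

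A simulation of 2,000,000 patients per setting, with 3-monthly scans and rates read 24 months after the first session, agrees: differences of +0.18 to +0.87 points (for example 35.01% against 35.20%, and 33.62% against 34.49%). The range is about +0.2 to +0.9.

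**5. OS.** Death does not wait for a scan, so the formula in step 3 applies directly. The documents give no OS assumption; 75-85% at 24 months is assumed.

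| True OS(24) | t0 = 1.23 | t0 = 1.99 | t0 = 2.91 |
|---|---|---|---|
| 75% | +1.11 | +1.81 | +2.66 |
| 85% | +0.71 | +1.15 | +1.69 |

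If deaths cluster early, the constant hazard fails. With a true OS of 80% and an assumed 1% to 5% dying before they qualify, PP shows 0.80/0.99 = 80.8% to 0.80/0.95 = 84.2%, that is +0.8 to +4.2 points.

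**The case against.** The strongest reply is that nothing rests on PP. The primary analysis uses CP, analyses default to ITT (SAP 6.1.1), no PP test is planned, the PP curves are drawn only if numbers allow, and exclusions will be listed with reasons, so early deaths and stops would be visible. A minimum-exposure set is a recognised sensitivity display. With 68 patients the standard error of a 50% rate is √(0.5 × 0.5/68) = 6.1 points, larger than any inflation above. All of this stands and limits the weight of the point. It does not remove the bias, which has one direction, and showing ITT alongside does not help when the gap between the curves is what misleads.

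Four stronger readings are tempting, and the documents do not support them:

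- *Every PP curve has a wholly event-free start that ITT lacks.* This is strict only for death. Progression is a RECIST finding first looked for at month 3 in all populations, so the ITT progression curve is also nearly flat early on. Progression found earlier would stop treatment and bar entry to PP, but no scan is scheduled to find it.
- *The PFS curves are inflated by 2 to 5 points.* That requires continuous detection of progression, which the scan schedule rules out.
- *Patients who stop for toxicity are deleted events.* Stopping is not an event on any of the three curves. Removing these patients is selection, of unknown direction and size.
- *PP is certain to look better than ITT.* With no early deaths the guaranteed period adds nothing, and the tumour-type exclusion could move the curve either way.

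**Conclusion.** The point holds as a modest defect in three supportive analyses. Selecting on a completed month of everolimus while counting from inclusion means that no PP patient can die before about 1.2 to 2 months, plus any gap to the first session. The resulting bias in OS, and in the death component of both PFS curves, is zero or upward.

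The likely size at 24 months is +0.2 to +0.9 points for the PFS curves and +0.7 to +2.7 points for OS. These ranges rest on a constant hazard, a 0 to 28 day gap, deaths at 10-20% of the PFS hazard and a true OS of 75-85%. None of these is in the documents, and the number of early deaths decides the real figure. The +1.8 to +4.9 points for PFS is a ceiling, not an estimate. A reader might infer that the trial's main conclusion is at risk; it is not, because the PP rule touches neither the primary endpoint, nor the CP set, nor the 31-of-68 threshold.

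**What to change.** Keep the PP definition and add a sentence to SAP 7.5: the PP curves start at a landmark 1 month after the first everolimus dose, include patients alive and on treatment at that date (and event-free for the two PFS curves), and report rates as conditional on reaching it. State whether a temporary interruption counts as being on treatment; SAP 7.6.2.1 already counts interruptions as treatment time. An alternative is to keep inclusion as the origin with delayed entry at the same date. In either case, say that a PP-ITT difference is not to be read as a treatment effect.

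Redefining PP as at least one dose is not sufficient. It still requires survival to a dose given 7 to 30 days after the session, plus any gap, so it shortens the guaranteed time without removing it. It would also bring PP close to the CP and tolerance sets, which already require a dose.

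Cost: no new data and no change to the sample size. SAP 7.1.2 allows changes before the database is frozen. PP rates become conditional and slightly less favourable, and with a landmark they are no longer on the same time axis as the ITT and CP curves.

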6.1.2 Population for tolerance analysis (SP)

It is defined as the ITT population that received at least one dose of everolimus. The safety criteria will be evaluated in this population.

A listing of patients excluded from the PP population will be provided with the reasons for exclusion.

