Overall survival will be defined as the time interval between the date of inclusion and the date of death regardless of the cause of death or the date of last news for living patients.

Tolerance to treatment will be assessed by:

- duration of treatment, doses received, dose reductions and deferrals
- Toxicities collected at each monthly visit, and described according to NCI-CTC version 4.0 criteria; Grade 3, Grade 4 and Grade 5 toxicities will be reviewed.
- the number and description of SAEs
- the evolution of the WHO performance index.

Calculation of the number of subjects needed

According to the literature, the median progression-free survival after embolization or chemoembolization ranges from 15 to 19 months with a progression-free survival rate of approximately 35%. As there is no information on progression-free survival in the literature, the hypotheses were built on the progression-free survival data.

The assumptions used to calculate the number of subjects are as follows:

H0: a 24-month progression-free survival rate of less than 35% is not acceptable

H1: A 24-month liver progression-free survival rate greater than 35% would demonstrate the utility of everolimus therapy with an expected 24-month liver progression-free survival rate of 50%,

To obtain a power of 80% with a first-species risk of 5% (one-sided), it is required to include 68 patients according to the assumptions established above (using the exact binomial distribution).

Taking into account a rate of lost to follow-up or patients not evaluable for any reason except death, 72 patients will be included.

3. Statistical analysis plan

Populations of analysis

Patients included in the study will be described (ITT) as well as patients not evaluable for the primary endpoint.

A patient is considered evaluable if he or she has received at least one dose of everolimus and one evaluation.

All efficacy analyses will be performed on a modified intention-to-treat basis (evaluable patients) included in the study regardless of eligibility criteria and treatment received.

Tolerability population: the ITT population that received at least one dose of the treatments.

In all cases of discontinuation, the patient remains in the intention-to-treat analysis. There is no exclusion period for a subsequent therapeutic trial.

Main analyses

A statistical analysis plan will be written prior to freezing the database.

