5.2 Treatment arm

There is a single study treatment arm consisting of:

- 1 to 2 embolization or chemoembolization sessions (sessions spaced 4 to 8 weeks apart).
- 10 mg/day everolimus (started 7 days after embolization or chemoembolization)

[figure not shown]
The maximum treatment period is 24 months.

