7.6 Assessment of tolerance

7.6.1 Embolization or chemoembolization

Population ITT

Treatment by (chemo)embolization will be described by:

- The number of embolizations (1 vs 2) per patient and the total number of embolizations performed
- The number of chemoembolizations performed and the type: by doxorubicin or streptozotocin
- The number and percentage of patients who had (of the population of patients who had at least one embolization/chemoembolization):
 - 1 single embolization session
 - 1 single chemoembolization session
 - 2 embolization sessions
 - 2 sessions of chemoembolization
- Cross-tabulation of the number of embolizations or chemoembolizations planned in the PCR (at inclusion) and the number of embolizations or chemoembolizations actually performed.

Will also be described (percentage on the total number of embolisations and/or chemoembolisations performed):

- The territory of (chemo)embolisations
- The presence of a complication during the procedure (No vs. Yes), and if so:
 - presence of hepatic arterial occlusion by dissection or spasm (No vs. Yes)
 - presence of bleeding at the puncture site (No vs. Yes)
 - presence of another complication (No vs. Yes)
- The presence of a post-session complication (No vs. Yes), and if yes, a listing of these complications.

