7.6.4 Toxicities

Population SP

Toxicities (graded according to NCI-CTC v 4.0) will be described by:

- The total number of patients by maximum grade of toxicity (grade 1-2-3-4-5);
- The number of patients and the maximum toxicity grade achieved (grade 1-2-3-4-5) by SOC and type of toxicity;
- Total number of patients by maximum grade of toxicity by grouping grades (grade 1-2 and grade 3-4-5);
- The number of patients and the maximum grade of toxicities achieved by grouping the grades (grade 1-2 and grade 3-4-5) by SOC and type of toxicities.

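### The SAP's graded toxicity tables cover only patients who took everolimus, so embolised patients who never start it are left out and the regimen's grade 3-5 rate is probably somewhat understated

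*SAP*

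**What the plan says.** **Population.** SAP 6.1.2, Population for tolerance analysis: "It is defined as the ITT population that received at least one dose of everolimus". It continues: "The safety criteria will be evaluated in this population". The exclusion listing specified under that heading names the per-protocol population, not SP.

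**Graded tables.** SAP 7.6.4 is headed Population SP: "Toxicities (graded according to NCI-CTC v 4.0) will be described by" maximum grade per patient, overall and by SOC and type, with grades 3-4-5 also pooled.

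**Protocol population.** Protocol XII.3, Populations of analysis: "Tolerability population: the ITT population that received at least one dose of the treatments".

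**Regimen.** SAP 5.2 lists two components of the single arm. The first is "1 to 2 embolization or chemoembolization sessions (sessions spaced 4 to 8 weeks apart"); the second is daily everolimus.

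**Entry to everolimus.** Protocol VI.2: "Everolimus will be started 7 days after embolization or chemoembolization or when liver toxicities have returned to a grade" of 1 or less. The same section adds: "Treatment should not be initiated beyond 30 days after embolization or chemoembolization".

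**Procedure safety.** SAP 7.6.1, on the ITT population, reports complications during the procedure as yes/no. It also reports "The presence of a post-session complication (No vs. Yes), and if yes, a listing of these complications". Percentages are taken over procedures, not patients.

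**The concern.** Tolerance of the treatment is a secondary objective, and Protocol XII.2 says that grade 3, 4 and 5 toxicities are part of it. The regimen under study begins with embolisation. A safety population that requires the second component leaves out anyone who received the first and did not reach the second.

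That would matter little if starting everolimus were unrelated to toxicity, but Protocol VI.2 links the two. I read its start rule as a delay for patients whose liver toxicity persists at day 7, with a cut-off at day 30. A patient whose liver toxicity does not settle in time, or who dies first, is embolised but never enters SP. Entry to the graded table then depends partly on having tolerated the first component, which pulls the reported grade 3-5 rate for the regimen downward. The SAP gives no reason for narrowing the protocol's definition.

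**Working it through.** **1. Who is in which output.** For a patient embolised but never given everolimus:

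| Output | Population stated | Is this patient in it? | Graded, per patient? |
|---|---|---|---|
| SAP 7.6.4 toxicities | SP | No | Yes |
| SAP 7.6.1 complications | ITT | Yes | No: yes/no, per procedure, with a listing of post-session complications |
| SAP 7.6.3 SAE summary | None stated | Possibly | Not specified |
| SAP 7.5.4 overall survival | CP, ITT and PP | Yes, in ITT | Not applicable |

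No output gives an NCI-CTC grade per patient for embolised never-starters. No listing of patients excluded from SP is specified either.

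**2. Figures in the plan.** The documents give no size for SP and no expected number of never-starters. The only anchor is the planned inclusion. The exact binomial rule of 31 or more successes in 68 has one-sided alpha 0.0461 under 35% and power 0.8019 under 50%, and 68/(1 - 0.05) = 71.6, rounded up to 72. These stated figures reproduce. None of them depends on the safety population.

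**3. Size of the understatement.** Let k be the number of embolised never-starters, p the grade 3-5 rate among starters and q the rate among never-starters. Assume that all 72 are embolised.

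- Rate in SP: p
- Rate in all treated: [p(72 - k) + qk]/72
- Difference: (k/72)(q - p)

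The difference is positive, meaning that SP understates, whenever q exceeds p. The start rule makes that likely but does not guarantee it. Taking the upper case q = 1 gives (k/72)(1 - p):

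| k | k/72 | p = 30% (assumed) | p = 50% (assumed) |
|---|---|---|---|
| 0 | 0 | 0 | 0 |
| 2 | 2.8% | 0.028 x 0.7 = 1.9 points | 0.028 x 0.5 = 1.4 points |
| 4 | 5.6% | 0.056 x 0.7 = 3.9 points | 0.056 x 0.5 = 2.8 points |
| 7 | 9.7% | 0.097 x 0.7 = 6.8 points | 0.097 x 0.5 = 4.9 points |

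In whole patients with p near 30%, SP against all treated reads:

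- k = 2: 21/70 = 30.0% against 23/72 = 31.9%
- k = 4: 20/68 = 29.4% against 24/72 = 33.3%
- k = 7: 20/65 = 30.8% against 27/72 = 37.5%

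Small departures from the formula come from rounding to whole patients.

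**4. Fatal events.** One toxic death between embolisation and the first everolimus dose would appear in the graded table as 0/71 instead of 1/72 (1.4%).

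**The case against.** The split looks deliberate. SAP 5.7.3 separates tolerability criteria for embolisation from those for everolimus and puts the NCI-CTC toxicities under everolimus. Protocol VI.1 treats lipiodol, doxorubicin and streptozotocin as non-investigational. For the question of what everolimus does to those who take it, an everolimus-exposed denominator is correct. The protocol phrase is also translated and not fully clear: a dose fits a drug better than a session of bland embolisation.

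Much of this stands, and it is why an everolimus-exposed table should be kept. It does not close the gap. SAP 7.6.4 is not limited to everolimus-attributed events or to events after the first dose. Protocol VI.1 says that tolerance of the embolisation sessions will be collected, and Protocol XI records all adverse events and grades toxicities by NCI-CTC. The plural in the protocol's population, with embolisation a component of the arm, makes the wider reading the more natural one.

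Three stronger readings are tempting, and the documents do not support them:

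- **The understatement is about 3 to 10 points for 2 to 7 never-starters.** That range is k/72, the share of missing patients. It equals the understatement only if no starter has a grade 3-5 event.
- **The excluded patients are those with the worst or fatal toxicity.** The start rule refers to liver toxicity only. Protocol VII.1 foresees patients with grade 3 or 4 non-haematological toxicity from the first session continuing on everolimus alone. Never-starters can also arise from refusal or the investigator's decision (Protocol IX).
- **Their harms go unreported.** Protocol XI requires all SAEs to be reported, attributable or not, during treatment and for 30 days after the last administration. SAP 7.6.1 lists post-session complications in ITT, and ITT overall survival counts early deaths.

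**Conclusion.** The point holds in a limited form. What is missing is a graded, per-patient toxicity rate for the whole regimen; harm is not left wholly unreported. The exclusion is related to outcome through the liver-toxicity condition, so the likely direction is an understated grade 3-5 rate.

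The size cannot be fixed from the documents because k is not given and may be zero. The figures above rest on three assumptions: all 72 patients embolised, a grade 3-5 event in every never-starter, and an assumed rate among starters. If some never-starters have no such event, the gap shrinks. The primary endpoint and its decision rule are unaffected. The plan should be changed, but this does not threaten the trial's main conclusion.

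**What to change.** - In SAP 6.1.2, define the safety population as all included patients who received at least one (chemo)embolisation session or at least one everolimus dose, in line with the natural reading of Protocol XII.3.
- Run SAP 7.6.4 on that population.
- Keep the everolimus-exposed subset, under its own name, for treatment duration, compliance, dose changes and an on-everolimus toxicity table.
- Correct the exclusion listing under 6.1.2 from the per-protocol population to the safety population.

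The cost is SAP wording and one additional toxicity table. The protocol already plans to collect the adverse event data, and under SAP 7.1.2 changes must be made before the database is frozen.
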